- c)** A 2-arm preference trial comparing post-release treatment completion in patients on OAT (further randomized to MMT vs BPN/NLX) vs no OAT in patients being treated for active or latent TB who are transitioning to the community.

AIM 2: To use data from specific aim 1 and publicly available data to conduct agent-based modeling for comparative and cost-effectiveness analyses of TB screening and treatment strategies among prisoners with and without HIV, incorporating the contribution of LTBI and prevalent TB on community transmission post-release.

2. Background: Describe the background information that led to the plan for this project. Provide references to support the expectation of obtaining useful scientific data.

Since 2003, Southeast Asia as a region has made major gains in reducing HIV infections and related morbidity and mortality by 37%, yet Malaysia is one of 4 countries in the region (all had major epidemics concentrated in PWIDs) where HIV mortality grew by >20%.¹ Drug injection, primarily of heroin, contributes significantly to evolving HIV epidemics, disability and mortality.² Criminalizing drug use rather than expanding risk reduction interventions has resulted in increasing imprisonment and concentration of people with HIV and opioid use disorders within prisons.^{3,4} Despite the overlapping and inextricable syndemics of HIV and PWIDs, HIV transmission continues unabated.⁵ Mathematical modeling studies of HIV prevention in countries where the HIV epidemic is either concentrated in or is generalizing from a PWID-driven epidemic, demonstrate that the combination of high coverage of opioid agonist and antiretroviral therapy is the best way to avert new infections,⁶ irrespective of the HIV prevalence among PWIDs.⁷ Opioid agonist maintenance therapies (OAT), however, are the most cost-effective.⁶ Moreover, prescribing antiretroviral therapy in HIV+ patients markedly reduces the development of active TB in patients with latent TB infection (LTBI).^{8,9}

[figure not shown]
3. Research Plan: Summarize the study design and research procedures using non-technical language that can be readily understood by someone outside the discipline. **Be sure to distinguish between standard of care vs. research procedures when applicable, and include any flowcharts of visits specifying their individual times and lengths.** Describe the setting in which the research will take place.

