in a 12HR combination since both isoniazid and rifapentine can damage the liver; CDC is calling for studies of 12HR in prisoners, but have not yet funded research. In the absence of studies of 12HR use in prisoners, it is crucial to assess both completion rates and tolerability (especially when high HCV prevalence is present).

Eligibility for Part B includes:

- 1) Meets inclusion criteria for Part A
- 2) Has latent TB (HIV+, or TST \geq 10mm (HIV-)) and no active TB disease
- 3) \geq 6 months before end of sentence to ensure option for treatment completion
- 4) AST/ALT <5 ULN, or AST/ALT <3 x ULN if TBil >2 x ULN
- 5) Not on a protease inhibitor (drug interaction with rifapentine)
- 6) No known porphyria
- 7) Not pregnant (women only).

Enrolled participants will undergo block stratified randomization, stratifying on four factors: a) CD4 <350 (if HIV+); b) HCV Ab status; c) ART status; and d) opioid dependence. After randomization and allocation to 12HR or 26H, participants will be provided 12HR weekly (12 weeks) and 26H daily (26 weeks) as directly observed therapy. Every 4 weeks, patients will be monitored for AST/ALT, adverse side effects and pregnancy. Premature treatment discontinuation will occur for any DAIDS Grade 4 toxicity, patient refusal to continue, or pregnancy (women only).

Study Design: TB Studies

Legend: LTBI=latent TB infection; H=isoniazid; HP=isoniazid + rifapentine; MMT= methadone maintenance treatment; BPN/NLX= buprenorphine/naloxone; OAT=opioid agonist treatment; ART= antiretroviral therapy; HCV= hepatitis C virus.

Part C:

A two-arm **preference trial** (no MAT, and methadone) of prisoners with opioid use disorders who are not or are currently being treated for TB and/or HIV, and are about to transition to the community and need to continue their treatment post-release. Patients may or may not be returning to Klang Valley and within 25 km of our research site. We anticipate enrolling 25-50 participants per arm.

Once consented, study participants will be provided an informed decision-making aid that will help them decide if medication-assisted treatment, specifically Methadone, is best for them. Participants will also have the option not to enroll in medication-assisted treatment.

[figure not shown]
Informed decision-making aid:

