saturation of themes is reached. Participants will undergo informed consent prior to participating, and will be compensated 50RM for their time.

Upon making an informed decision using the SDM developed from the focus groups, those that choose methadone maintenance treatment (MMT) will initiate 5 mg of methadone, 3-4 months prior to release from prison. The dose will increase in 5 mg increments every 7 days (as tolerated) until the daily dose is escalated to at least 80 mg or optimal dose before the date of release. Patients prescribed MMT will receive medication daily in prison, and will receive their medications weekly in form of take-way dosing. MMT will be dispensed at the community research site. All participants will be maintained on medication-assisted treatment and will receive follow-up care for 6 months after release from prison.

After a baseline assessment, our research assistant (RA) would meet the participant at the prison on the day of release to undergo a brief assessment, urine testing and to introduce the patient to our community research site to ensure that s/he can find the site after release and take the participant home so that our research assistants can know where the person is living/residing. This process will also improve trust between the research staff and the participant. Thereafter, all participants will be seen monthly, where they will undergo urine screening and be assessed for alcohol and drug use using timeline follow-back (TLFB), appointments for HIV and/or TB, adherence to HIV and/or TB medications, assessments of legal, employment, family issues using the Lite version of the Addiction Severity Index (ASI), depressive symptoms, health-related quality of life (HRQoL), satisfaction with their treatment. They will also be assessed for diversion (and urine testing).

The primary outcome will be the proportion completing treatment for active or LTBI. Secondary analyses will compare Kaplan Meier curves using Cox proportion hazards and time to discontinuation. TB treatment adherence will also be measured using MEMS caps and analyzed as we have done previously in TB patients in Ukraine

Eligibility for Part C includes:

- 1) Meets inclusion for part A, if possible
- 2) Opioid dependence
- 3) Has LTBI or active TB disease (based on screening in Part A), or no TB
- 4) Returning to live in Kuala Lumpur/Klang Valley region (within 25 km of Kerinchi research site), if possible
- 5) ≤ 6 months before end of sentence

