Part A: New intakes from Kajang Prison will be recruited (80-120) per day. Mandatory HIV testing is done on all prisoners. HIV prevalence is 5%. All HIV+ prisoners upon entry will be approached for informed consent. For Part B, only prisoners who have >9 months (preferably 12 months) remaining on their prison sentence will be approached for recruitment. All subjects are expected to be Southeast Asians/Pacific Islanders. While women will represent only 10% of the sample, they will be included. The minimum age is 18 years of age, thus children 18-21 years old will be eligible for participation. Currently, only 2% of HIV+ prisoners are between 18-21 years. For part C, prisoners who have less than 90 days remaining on their prison sentence, but more than 90 days of TB treatment remaining will be approached for recruitment. They must be at least 18 years old, have latent TB infection defined by TST \geq 5mm (HIV+), or TST \geq 10mm (HIV-), return to live in Klang Valley (within 25 km of Kerinchi research site), and AST/ALT <5 X ULN.

Aim 2 will not include Human Subjects. Data analysis only.

6. Subject classification: Check off all classifications of subjects that will be specifically recruited for enrollment in the research project. Will subjects who may require additional safeguards or other considerations be enrolled in the study? If so, identify the population of subjects requiring special safeguards and provide a justification for their involvement.

 Children	 Healthy	 Fetal material, placenta, or dead fetus
 Non-English Speaking	 Prisoners	 Economically disadvantaged persons
 Decisionally Impaired	 Employees	 Pregnant women and/or fetuses
 Yale Students	 Females of childbearing potential	

NOTE: Is this research proposal designed to enroll children who are wards of the state as potential subjects? Yes No (If yes, see Instructions section VII #4 for further requirements)

7. Inclusion/Exclusion Criteria: What are the criteria used to determine subject inclusion or exclusion?

Inclusion and Exclusion Criteria:

1a: inclusion:

- Above 18 years old
- Malaysian Citizen
- Newly admitted (<2 days)
- Able to provide consent
- Absence of active TB within 2 years of enrollment

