- \geq 3 month prison sentence

1b inclusion:

- Meets inclusion criteria for part A
- Has latent TB (HIV+, or TST \geq 10mm (HIV-)) and no active TB disease
- >6 months before end of sentence to ensure option for treatment completion

- AST or ALT <5X ULN, or AST/ALT <3x ULN if TBil >2x ULN
- Not on a protease inhibitor (drug interaction with rifapentine)
- No known porphyria
- Able to provide informed consent

1c inclusion:

- Meets inclusion criteria for Part A, if possible
- Opioid dependence
- Has latent TB (HIV+, or TST \geq 10 mm (HIV-)), or active TB infection, or no TB
- Returning to live in Kuala Lumpur/Klang Valley region (within 25 km of Kerinchi research site), if possible
- AST/ALT <5X normal
- \leq 6 months remaining in prison
- Able to provide informed consent

Exclusion Criteria: Pregnant women or women planning to become pregnant will be excluded if we implement methadone or buprenorphine during pregnancy, the infant born to the mother is highly (>60%) likely to develop an infant abstinence syndrome that is avoidable by not providing MMT. If a woman becomes pregnant during the course of the study, MMT will not be discontinued if she is receiving it as withdrawal has resulted in pre-term labor. For women preferring not to be OAT, but who relapse to drug use, entry onto MMT will not be an exclusion criteria for remaining in the study.

8. How will **eligibility** be determined, and by whom?

Eligibility will be determined by the Research Assistants (RAs) hired by the University of Malaya – CERIA to work on this study. An eligibility screening form will be developed into REDCap, a data collection and management application that will be used by the local RAs.

Prior to enrollment, laboratory testing will be completed to ensure normal LFTs and urine testing will be completed to ensure that female participants are not pregnant.

9. **Risks:** Describe the reasonably foreseeable risks, including risks to subject privacy, discomforts, or inconveniences associated with subjects participating in the research.

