
Part B: In CDC's original non-inferiority trial of 26H v 12HR, treatment completion differed significantly (67.0% v 82.1%); however, there were no HIV+s (and therefore no ART prescribed)

and HCV infection was <3%. Therefore tolerability for a longer exposure to 26H may decrease completion further. We will compare the proportion completing TB preventive therapy (no adverse side effects) for the two groups and control for any confounders that may differ after randomization. Using an alpha=0.05 and power=0.8 and a 20% difference (most conservative), we would need 118 per arm. We hypothesize, however, that 26H will be tolerated even less based on studies of IPT hepatotoxicity in a RCT of isoniazid in prisoners (21% in with HCV)⁴² and HCV+ patients (correlated with longer IPT exposure).⁴³⁻⁴⁵ Thus, even increasing the difference in treatment completion to 20% (still conservative), the sample size would need to be 164. Thus, we will conservatively enroll 177 per arm or 354 patients total. We will analyze the data two ways, including ITT as a difference in proportion of treatment completion used in RCTs. In order to discern factors associated with differences in treatment completion, we will treat the entire recruited sample as a cohort and using Cox regression, examine time to treatment discontinuation between the two groups using Cox Proportion Hazards as well as examine the independent factors associated with treatment discontinuation (e.g., being on ART, HCV status, baseline AST/ALT, CD4 strata, etc).

Part C: Eligibility will be having no TB disease, TB disease or LTBI, on TB medications that must be completed after release, and meet pre-incarceration DSM-V criteria for opioid dependence. We will compare a control group of prisoners choosing no OAT and compare them to OAT patients. Even though we anticipate 15-20% attrition, we will count missing=failure to be conservative and will censor the data based on the mid-point between the last and the missed visit. The primary outcome will be the proportion completing treatment for active or LTBI. Secondary analyses will compare Kaplan Meier curves using Cox proportion hazards and time to discontinuation. TB treatment adherence will also be measured using MEMS caps and analyzed as we have done previously in TB patients in Ukraine.

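### Part C admits people with no TB course to complete, leaves the denominator of its primary outcome undefined, and compares self-chosen OAT and no-OAT groups with no stated adjustment

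*Combined protocol and SAP*

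**What the plan says.** The text on who enters Part C falls into two groups.

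Admitting people without TB:
- Section V.3, Eligibility for Part C: "Has LTBI or active TB disease (based on screening in Part A), or no TB".
- Section V.7, 1c inclusion: "or active TB infection, or no TB".
- Section V.3, Part C design: "prisoners with opioid use disorders who are not or are currently being treated for TB and/or HIV", who are "about to transition to the community and need to continue their treatment post-release".
- Section V.12, Part C: "Eligibility will be having no TB disease, TB disease or LTBI, on TB medications that must be completed after release". This sentence opens by admitting people without TB and then refers to TB medication.

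Describing only people with TB or LTBI, or on treatment:
- Section V.1, Aim 1c: OAT against "no OAT in patients being treated for active or latent TB who are transitioning to the community".
- Section V.5, Subject Population: "less than 90 days remaining on their prison sentence, but more than 90 days of TB treatment remaining".
- Section VII.3, Part C: recruitment from Part A participants with latent or active TB.

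Sections V.3 and V.12 both give the primary outcome: "The primary outcome will be the proportion completing treatment for active or LTBI". Planned enrolment is 25-50 per arm (Section V.3). After a decision aid, participants choose methadone or no medication-assisted treatment. Section V.12 then compares those choosing no OAT with OAT patients, and adds Kaplan-Meier and Cox analyses with no covariates named. Expected attrition is 15-20%, with missing counted as failure. Confounder control is mentioned only for the randomised Part B.

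**The concern.** A completion proportion needs a defined set of people who have something to complete. Here eligibility is wider than the outcome, and no section says whether people without a course are left out, counted in some way, or analysed on another endpoint. The analyst would have to settle the denominator of a primary outcome, possibly after seeing the data, and the evaluable number would fall below 25-50 per arm by an amount nobody has set.

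The comparison has a second weakness. People who choose methadone may differ from those who decline it in addiction severity, HIV status, type of TB or motivation, and any of these may affect completion. An unadjusted difference cannot separate these from an effect of OAT.

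**Working it through.** **The plan's own figure.** The 25-50 per arm cannot be reproduced, because Part C has no alpha, power, completion rate or target difference. The Data and Safety Monitoring section mentions a difference of about 40% between a control and two intervention groups, but labels it Part B. If it were meant for Part C (an assumption), then with two-sided alpha 0.05, power 0.8 and 30% v 70% completion:

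n = [1.96·√(2·0.5·0.5) + 0.842·√(0.3·0.7 + 0.7·0.3)]² / 0.4² = (1.386 + 0.545)² / 0.16 = 23.3, so 24 per arm.

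The lower end of the range is compatible with that difference, but the documents do not connect the two.

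**Share with no TB.** Planning figures are more than 80% TST-positive (Section V.3, Part B), and LTBI 84% with active TB 10-15% (Section V.12, Part A).
- From the TST figure: below 100 − 80 = 20%.
- From LTBI alone, active cases inside the 84%: 100 − 84 = 16%.
- If LTBI and active TB are exclusive: 100 − 84 − 10 = 6%, or 100 − 84 − 15 = 1%.

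The no-TB share is therefore probably below about 20%. Part C may also recruit outside Part A, so this is a guide only.

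**Share with no course running past release.** This is the share that matters for the outcome, and the documents do not give it. Two statements suggest that it may be much larger than 20%:
- Section V.3 (Part B) reports that preventive therapy reaches few prisoners with LTBI.
- Part B is a study source of LTBI treatment. It requires at least 6 months of sentence remaining (more than 9 in Section V.5) so that treatment can be completed. Its courses last 12 or 26 weeks; 26 × 7 = 182 days, about 6 months. Started on time and uninterrupted, they end in prison or about at release.

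**Precision.** Assume 70% completion in both arms and equal arms of n evaluable participants. The half-width of the 95% confidence interval for the difference is 1.96·√(2·0.7·0.3/n).

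| Share without a course (assumed) | Evaluable per arm | Half-width, points | Non-completers, both arms (0.3·2n) |
|---|---|---|---|
| 0% | 50 to 25 | 18.0 to 25.4 | 30 to 15 |
| 20% | 40 to 20 | 20.1 to 28.4 | 24 to 12 |
| 50% | 25 to 12.5 | 25.4 to 35.9 | 15 to 7.5 |

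The last column limits how many covariates a model can carry.

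**Self-selection.** With no true OAT effect, one binary prognostic factor produces an apparent difference equal to its imbalance between arms times its gap in completion. The documents give neither input. With an assumed imbalance of 20-40 points and a gap of 10-30 points, the result runs from 0.2·0.1 = 2 points to 0.4·0.3 = 12 points, with either sign, and is 0 if the arms are balanced. This shows scale only.

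**The case against.** The natural reading of the outcome leaves out anyone without a course. Part C is small and openly called a preference trial, so self-selection is disclosed. Nothing prevents covariates in the Cox model.

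Most of this is fair but does not close the gap. The natural reading is not written down, and under it the 25-50 per arm still overstates the evaluable number. The preference label discloses self-selection without dealing with it. The primary comparison of proportions has no adjustment, and the Cox analysis names no covariate. Randomising methadone v buprenorphine/naloxone within OAT, which Aim 1c still mentions, would not help with OAT v no OAT.

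Three stronger readings are tempting, and the documents do not support them.
- A reader might infer that people without TB would count as treatment failures. No section says so; the missing-equals-failure rule is tied to attrition.
- A reader might infer that the Part C design paragraph in Section V.3 contradicts itself. It speaks of TB and/or HIV, so someone without TB who is on HIV treatment satisfies it. The clear conflict is between the eligibility lists and Sections V.1, V.5 and VII.3.
- A reader might infer that self-selection favours OAT. The direction is unknown.

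**Conclusion.** The point holds and should be fixed. The population text conflicts across sections, the denominator of the primary outcome is not stated, and the only planned comparison of self-chosen groups has no stated adjustment. These findings rest on the text and are secure.

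The size is less certain. The share without a course running past release is unknown; the figure of about 20% limits only the share without TB. The half-widths (18-25 points with everyone evaluable, 20-28 at 20% without a course, 25-36 at 50%) rest on an assumed 70% completion, equal arms and assumed shares. The size and direction of any selection effect cannot be derived from the documents.

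**What to change.** (a) Reconcile Sections V.1 (Aim 1c), V.3 (Part C design and eligibility), V.5, V.7 (1c), V.12 (Part C) and VII.3. Define the primary analysis set as participants who, at consent and before choosing an arm, are on a TB or LTBI course scheduled to run past release. Keep those who stop later as failures. Do not define the set by status at release: consent precedes the decision aid and methadone starts 3-4 months before release, so that status follows the choice. Analyse other participants separately on outcomes already collected, such as urine-tested drug use and retention. State the expected size of the primary set.

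(b) Prespecify an OAT v no-OAT comparison adjusted for two or three variables known before the choice: active TB v LTBI, HIV status, and addiction severity only if recorded at baseline. Section V.3 lists ASI-Lite among the monthly visits after release, and a value taken after the choice should not be adjusted for. Show the unadjusted result alongside and call the comparison observational. If the primary set is too small to support adjustment, report completion descriptively with confidence intervals and draw no comparative conclusion.

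(c) Minor: report attrition by arm with one sensitivity analysis to missing=failure, since that rule is conservative between arms only if loss is not greater without OAT. State that mid-point censoring applies only to the time-to-event analysis.

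The cost is an amendment to align the sections and some analysis-plan text, with no new data unless addiction severity is not yet recorded at baseline. The primary set will be smaller, possibly much smaller, and intervals wider; that loss is already in the design. Unmeasured selection remains after adjustment.
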